Pilot study to compare serology results from blood collected using Tasso-SST OnDemand device
compared to venipuncture

Document Date: November 23, 2021

NCT04713748

Purpose of the Study

The purpose of this pilot study is participant user acceptance testing of the Tasso-SST OnDemand device to collect blood for antibody testing. The study will also compare antibody testing results from blood collected using the Tasso-SST On-Demand device compared to blood collected by phlebotomy.

Background & Significance

Coming into a research clinic site is an exposure risk for participants and staff. Coming into a research clinic site is a study burden for participants. The Tasso-SST OnDemand device could provide a means for participants to collect samples at home and ship directly to the lab.

The Tasso-SST OnDemand device, specifically the SST tube, is not approved for sars-cov-2 serology. We are testing it in a pilot study to confirm similar result from serum processed from blood collected by Tasso-SST OnDemand device and standard venipuncture (collection by standard venipuncture is part of study procedures for the MURDOCK C3PI Study (Pro00105703)). Results from this pilot study will help inform the possibility of at-home specimen collection for serology testing. We also hope to gain insight from participants about the instructions, and their willingness and ability to use it on their own, at home, in the future.

Design & Procedures

Prospective participants will receive an invitation from the PI via recruitment email to review the electronic consent form in Duke REDCap. Participants are instructed to call or email the Duke CTSI Office in Kannapolis with any questions. We will use the e-consent module in Duke REDCap. We have engaged DOCR to ensure that the e-consent used for the study is compliant. The identity of the consenting participant will be verified by the following steps: 1) participant will enter first and last name, date of birth, and email address, which will be verified against our records on file. Study team will be alerted to any discrepancies. The identity of participants will be further confirmed at the study visit, and done prior to completion of any study procedures.

At the study visit, participants will collect a small blood sample using the Tasso-SST OnDemand device during a serology blood draw visit already scheduled for the MURDOCK C3PI Study (Pro00105703). Participants will be provided a kit that includes written, step-by-step instructions that include pictures. Participants will also have the option to watch a brief video on using the device, available online at the Tasso website, prior to collection (<https://www.tassoinc.com/tasso-sst-help>). The Tasso-SST OnDemand device collects whole capillary blood, at a minimum volume of 80ul. In section 3100 of this application as the iRIS does not take any decimals' and hence have 1ml as the max amount of blood drawn.

A standard blood draw will also be done as described in the MURDOCK C3PI Study research summary and informed consent (Pro00105703). Both blood samples will be spun and processed for serum. Serum will be frozen and shipped to the lab at Duke for antibody testing. Antibody results will be compared between the two methods.

Participants will be sent a brief survey to learn about their experience using the Tasso-SST OnDemand device.

Selection of Subjects

Inclusion Criteria

- Must be a study participant enrolled in the MURDOCK C3PI Study (Pro00105703), participating in the testing cohort of the study.
- Participants are therefore 18 years of age or older, and willing to read and complete the consent process.

No exclusion criteria; however, only up to 100 participants will be enrolled. If more than 100 participants sign consent, some interested participants may not take part in the study.

Study Interventions

Participants will collect blood on their own using the Tasso-SST OnDemand device, following instructions provided in the kit. The Tasso-SST OnDemand device collects whole capillary blood, at a minimum volume of 80ul. Collected blood is spun into serum, frozen and shipped to the lab for analysis.

The Tasso-SST OnDemand device sticks to the skin with a light adhesive. When the button is pressed, a vacuum forms and a lancet pricks the surface of the skin. The vacuum draws blood out of the capillaries and into a tube attached to the bottom of the device.

Data Analysis & Statistical Considerations

We will evaluate correlation between results from blood collected by the two methods in this pilot study and qualitatively exam participant survey results. Summary statistics will be generated for survey responses, and qualitative data will be reviewed.

Data & Safety Monitoring

Participants will be instructed to follow the provided directions, step-by-step, and have the option to watch an instructional video prior to use. Participants will be observed by trained staff in a clinical research setting while using the Tasso device. The participant may choose not to participate at any time.

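### Does comparing only clinic-collected, staff-observed, spun-and-frozen serum undercut the pilot's at-home aim?

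*Combined protocol and SAP*

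**What the plan says.** The Background & Significance section gives the motivation: "The Tasso-SST OnDemand device could provide a means for participants to collect samples at home and ship directly to the lab". The same section states what the serology comparison is for, namely to "confirm similar result from serum processed from blood collected by Tasso-SST OnDemand device and standard venipuncture". It then says how the findings will be used: "Results from this pilot study will help inform the possibility of at-home specimen collection for serology testing". Separately, it hopes to learn from participants about the instructions and about "their willingness and ability to use it on their own, at home, in the future".

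Design & Procedures places the Tasso collection at a blood draw visit already scheduled for the parent study, with a standard venous draw as well. On handling it says "Both blood samples will be spun and processed for serum. Serum will be frozen and shipped to the lab at Duke for antibody testing". Study Interventions repeats that order for the Tasso sample and says that participants take the sample themselves, guided by the kit instructions. Data & Safety Monitoring adds: "Participants will be observed by trained staff in a clinical research setting while using the Tasso device".

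The Data Analysis & Statistical Considerations section plans this for the serology: "We will evaluate correlation between results from blood collected by the two methods in this pilot study". It names no collection or handling conditions and contains no statement about how far the result can be generalised. Neither does any other section.

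**The concern.** The motivating route is a participant at home who sends the sample straight to the laboratory. The tested route is a participant in a clinic, watched by staff, whose sample is spun and frozen before it travels. The two differ in setting, in observation and in what is shipped.

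The conditions are also spread over several sections. The observation by staff appears only under Data & Safety Monitoring, away from both the at-home aim and the analysis. Someone who read only the analysis section would see a comparison of two methods with no conditions attached.

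At stake is over-interpretation. If the two methods compare well, a reader deciding on home serology might take the result as covering unobserved collection, transit and processing together. The data would bear only on Tasso self-collection versus venipuncture under the conditions used.

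**Working it through.** The documents give no power, precision or margin figure tied to this point, so there is no figure of the plan's own to reproduce. The check sets each step of the motivating route beside what is done and what is claimed.

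| Step | Motivating route (Background & Significance) | Pilot (other sections) | What the plan claims to show |
|---|---|---|---|
| Who collects | Participant | Participant, using the kit instructions (Study Interventions) | Participants' experience, by survey |
| Setting | Home | Scheduled clinic visit (Design & Procedures) | Future home use, through participants' views only |
| Observation | Not described | Trained staff observe (Data & Safety Monitoring) | No claim about unobserved use |
| Shipment | Participant to laboratory; handling not described | Spun, frozen, then shipped (Design & Procedures; Study Interventions) | Similar results from processed serum |

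**Serological target against procedures.** The target is worded in terms of serum already processed from blood taken by each method. Spinning and freezing both samples is consistent with that target: it compares collection methods without adding a planned difference in handling. The design answers the question that the plan puts to it.

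**Claim about home use against evidence.** The claim is that pilot results will help in judging whether home collection is possible. Showing that serum from a self-operated Tasso device gives results similar to venous serum is one necessary part of that judgement. The claim does not say that the remaining parts are covered.

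**Ability at home.** The wording about using the device at home, "willingness and ability to use it on their own, at home, in the future", describes insight sought from participants. The plan provides a survey for their experience. It is not an aim of the antibody comparison, so it does not widen the gap in that comparison.

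**Counts.** Planned pairs collected unobserved: 0. Planned pairs shipped before spinning: 0. The cap is 100 participants. The documents do not say where the samples are spun or how soon after collection, so a delay before spinning can be neither asserted nor excluded.

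**Can the gap be given a numerical size?** One attempt is to assume agree/disagree scoring and agreement in every pair. The exact lower limit of the two-sided 95% interval is then 0.025^(1/n):

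- n = 100: 0.9638, so 1 − 0.9638 = 3.6 percentage points
- n = 50: 0.9289, so 1 − 0.9289 = 7.1 percentage points
- n = 30: 0.8843, so 1 − 0.8843 = 11.6 percentage points

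The 50 and 30 are illustrative, because the documents give only the cap. The arithmetic is right, but it does not measure scope. It gives the precision of an agreement proportion, and the plan specifies a correlation. With no samples from a home route, the study could not show a home-route loss of any size, so a threshold of 3.6, 7.1 or 11.6 points has no special meaning. The two zeros are the only relevant figures, and they follow from procedures that the plan states openly.

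**The case for a change.** The strongest case for acting is that the limit is real, is written down nowhere, and would take one sentence to state. The at-home aim refers expressly to serology testing, so the antibody results, and not only the survey, are tied to home use. A cautious phrase does not tell the reader which part of the home route is being informed, and finding out means combining several sections. The sentence would change no procedure, sample size or analysis.

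Most of the factual part stands. There is no explicit limitation statement, and no home-collected or pre-processing-shipment sample is planned. A report that presented the result as validating the whole home route would overreach.

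Three things keep this from being a fault in the plan. First, the plan makes no such overreaching claim: it calls itself a pilot, words the home-use claim cautiously and places home use in the future. Second, the conditions are disclosed in a very short document, so a reader does not have to guess at them. Third, the collection step is partly represented, because participants operate the device themselves; what goes untested is the absence of observers, the home setting and shipment before processing. Nor would a sentence about agreement fit the analysis section as it is written, since only a correlation is planned there. Whether a correlation is the best summary is a separate question.

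**Conclusion.** The concern does not hold as a fault in the plan. The serology comparison is confined to observed, clinic-collected samples that are spun and frozen before shipment, but that matches the stated target of comparing processed serum by collection method. The at-home wording claims no more than a contribution to a later decision. Carried out as written, the plan's procedures answer the comparison question that it sets.

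In size, 0 of up to 100 planned pairs test unobserved collection and 0 test shipment before spinning. Both zeros follow from the stated design and contradict nothing in the plan. No rule or figure needs correcting.

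This conclusion rests on two readings of the Background & Significance section: that its reference to processed serum defines the serological target, and that its at-home sentence is a cautious statement of purpose and not a promise to validate the home route. It would change if the results were reported as covering unobserved collection or transit. The documents give no information on whether either would alter the antibody results.

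### Does the acceptance survey need a stated send date, a recipient rule for people who stop or get no sample, and a non-response rule?

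*Combined protocol and SAP*

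**What the plan says.** The Purpose of the Study section puts acceptance first: "The purpose of this pilot study is participant user acceptance testing of the Tasso-SST OnDemand device to collect blood for antibody testing". The antibody comparison is introduced after it as a further aim. The Background & Significance section adds that the team wants participants' views on the instructions and on "their willingness and ability to use it on their own, at home, in the future".

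The survey itself appears in two places. Design & Procedures, after describing device collection and the standard draw, states: "Participants will be sent a brief survey to learn about their experience using the Tasso-SST OnDemand device". Data Analysis & Statistical Considerations says the survey results will be examined qualitatively, and then: "Summary statistics will be generated for survey responses, and qualitative data will be reviewed".

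Three other statements bear on who might be surveyed or what else is known about device use:

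- Selection of Subjects caps enrolment at 100 and notes: "If more than 100 participants sign consent, some interested participants may not take part in the study".
- Data & Safety Monitoring allows people to stop: "The participant may choose not to participate at any time".
- The same section says of collection: "Participants will be observed by trained staff in a clinical research setting while using the Tasso device".

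Nowhere in the supplied text is there a survey date or window, a denominator, a reminder procedure or a rule for unanswered surveys.

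**The concern.** Acceptance is the first-named aim, and the survey is the only source of acceptance data whose analysis is described. Staff watch the collection, but the plan does not say that what they see is recorded or analysed. How completely the survey covers the people who tried the device therefore matters.

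The word for the recipients is used loosely. Selection of Subjects applies it to people who sign consent yet may never take part, and Data & Safety Monitoring lets a person stop at any time without saying whether the survey still follows. Because the survey asks about using the device, site staff might skip someone who stopped part-way or drew no blood. Such people could well be less favourable than the rest, so leaving them out would tend to make acceptance look better than it was. Counts can be reconstructed later, but the views of people never asked cannot be reliably recovered.

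Non-response would act in the same direction if dissatisfied people reply less often, and a summary of returned surveys alone would not reveal it.

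**Working it through.** **What the text leaves open.** The plan has no figure to reproduce: it gives no expected response, stopping or failure rate, and the 100 is an enrolment cap with no statistical derivation. The first step is to read the survey sentence against each group.

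| Group | Is the survey sentence clear for them? |
|---|---|
| Used the device, sample obtained | Yes |
| Used the device, no sample or too little | Yes on the plain reading: the sentence sets no condition about a sample, and they have used the device |
| Stopped during collection | Not stated |
| Consented above the cap, never took part | They have no experience of the device to report |

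Only the third row is open. The fourth shows loose wording but poses no threat to the acceptance result. On timing, the position of the sentence and its subject both place the survey after use; only the interval is missing.

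**How much missing answers could matter.** All inputs except the cap of 100 are assumptions for illustration, including a yes/no measure of being favourable, which the plan does not define.

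- N = 100 people attempt collection.
- A share s gives no answers, either because they were not sent the survey or because they did not return it.
- 90% of those who answer are favourable.

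Lower bound (all missing people unfavourable) = 0.9 × (1 − s). Upper bound (all missing people favourable) = 0.9 × (1 − s) + s. The width is s.

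- s = 0.10: 81 of 90 favourable; bounds 0.81 to 0.81 + 0.10 = 0.91.
- s = 0.20: 72 of 80 favourable; bounds 0.72 to 0.72 + 0.20 = 0.92.
- s = 0.40: 54 of 60 favourable; bounds 0.54 to 0.54 + 0.40 = 0.94.

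The reported 90% exceeds the true share by s × (0.9 − p), where p is the favourable share among the missing. With p = 0.5 this is 0.10 × 0.4 = 4 points and 0.20 × 0.4 = 8 points. With p = 0.9 it is zero.

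**Sampling error for scale.** The 95% Wilson interval must use the number who answer, not 100. For 81/90 it is 82.1% to 94.6% (12.6 points wide). For 72/80 it is 81.5% to 94.8% (13.4 points). This gives no safe cut-off for missing answers, because selection adds to sampling error and is not absorbed by it.

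**What can be recovered without a change to the plan.** The number attempting collection, the number sent the survey and the number returned can all be counted after the event. With those counts, the bounds above can be worked out for any survey item.

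**The case for a change.** The strongest argument for changing the plan is that an omission at the sending stage cannot be undone. If staff decide case by case that a person who stopped had no experience worth asking about, those answers are lost, and they concern the study's first aim. One sentence would prevent this at almost no cost. It would add no visit or sample, and email addresses are already entered at consent, although there for checking identity.

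Part of this stands. The plan does not say what happens to people who stop during collection, and a sentence confirming that everyone who attempts collection is surveyed unless they decline further contact would be harmless and tidy.

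The rest does not carry. The harm depends on an exclusion that the text does not contain, since the survey sentence is unconditional. Non-response is a matter of reporting, and the counts remain available. No consequence of the missing send date has been shown. Ability to use the device also does not rest on the survey alone: collection takes place in front of trained staff, and a missing device sample will show up when results are paired with the venous draw. The supplied text is also incomplete. Consent pages were removed, and Design & Procedures points to material elsewhere ("In section 3100 of this application"), so some of these details may already be written down.

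**Conclusion.** The observation is correct as far as it goes: send date, treatment of people who stop during collection, and reporting of non-response are not stated. It is a gap that analysts and site staff fill sensibly, not a fault in the method. Followed as written, the plan sends the survey to participants who used the device and summarises the replies descriptively. No rule in it produces a wrong result, and no threshold or test depends on the answer.

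The possible size is known only under assumptions. With 90% of respondents favourable, the range for all 100 is 10 points wide if 10 people are missing and 20 points wide if 20 are. The reported figure would be 4 or 8 points too high if half of those missing were favourable, and unbiased if they resembled the rest. The documents give no basis for choosing among these cases. The conclusion rests on reading the survey sentence as covering all who try the device, and on the final report giving the numbers attempted, sent and returned beside the summary statistics, which is ordinary practice.

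### No rule on antibody status governs who fills the up-to-100 places, and results are compared only by one overall correlation, so similarity could be concluded for a status group hardly tested

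*Combined protocol and SAP*

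**What the plan says.** Eligibility under Selection of Subjects rests on parent-study membership: "Must be a study participant enrolled in the MURDOCK C3PI Study (Pro00105703), participating in the testing cohort of the study". Adult age and willingness to consent follow from that. The section continues "No exclusion criteria" and sets a cap, "only up to 100 participants will be enrolled". On over-subscription it says "If more than 100 participants sign consent, some interested participants may not take part in the study", without saying how those people are chosen. Design & Procedures has the principal investigator send invitations by email. The device sample is taken "during a serology blood draw visit already scheduled for the MURDOCK C3PI Study (Pro00105703").

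Background & Significance gives the aim of the comparison: "We are testing it in a pilot study to confirm similar result from serum processed from blood collected by Tasso-SST OnDemand device and standard venipuncture". Purpose of the Study puts user acceptance first: "The purpose of this pilot study is participant user acceptance testing of the Tasso-SST OnDemand device to collect blood for antibody testing". The comparison of antibody results is added as a further aim.

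Data Analysis & Statistical Considerations plans a correlation between the two sets of results, plus summaries of the survey. It plans no analysis by antibody status. The documents give no expected prevalence, no minimum number of positives or negatives and no agreement threshold. They do not say whether the assay result is qualitative or quantitative.

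**The concern.** Agreement among antibody-negative people says nothing about positives missed in device serum. Agreement among antibody-positive people says nothing about false positives. To support a general statement of similarity, the comparison needs a reasonable number of pairs of each status, and nothing in the plan secures that or would show that it is lacking.

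If one status dominates, a single overall summary is driven by that group. If results are binary and all identical, a correlation cannot be computed at all. If they are quantitative and the range is narrow, it is hard to interpret. The pilot could then be reported as confirming similarity that was barely examined in one group, and its results are meant to inform at-home collection for serology.

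**Working it through.** There is no sample-size calculation to reproduce. The figure of 100 is a cap, with no margin, power, expected agreement or expected prevalence behind it. The check asks how much 100 pairs would show about the smaller status group.

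**Inputs.** N = 100 pairs is the stated maximum (Selection of Subjects). The share in the smaller group is not in the documents, so a range is assumed. Results are taken as positive or negative, which is also an assumption.

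**Step 1: number in the smaller group.** Binomial with N = 100.

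| Assumed share | Expected number | 95% range | Chance of fewer than 10 |
|---|---|---|---|
| 2% | 2 | 0–5 | nearly 100% |
| 5% | 5 | 1–10 | 97% |
| 10% | 10 | 5–16 | 45% |
| 20% | 20 | 12–28 | 0.2% |
| 30% | 30 | 21–39 | nearly 0% |
| 50% | 50 | 40–60 | nearly 0% |

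No minimum enrolment is stated, so a smaller study would give fewer.

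**Step 2: what perfect agreement would show.** When all n pairs agree, the exact (Clopper–Pearson) two-sided 95% lower limit is 0.025^(1/n).

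- n = 2: 15.8%
- n = 5: 47.8%
- n = 10: 69.2%
- n = 20: 83.2%
- n = 30: 88.4%
- n = 50: 92.9%

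**Step 3: chance of seeing a problem.** If device serum gave a wrong result in a fraction d of the smaller group, the chance of at least one discordant pair is 1 − (1 − d)^n. Both values of d are illustrative.

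- d = 10%: 41% with n = 5, 65% with n = 10, 88% with n = 20.
- d = 20%: 67% with n = 5, 89% with n = 10, 99% with n = 20.

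**Step 4: what the cap can support.** With no discordant pairs, the n needed for a lower limit of at least L is ln(0.025)/ln(L), rounded up. This is 17 for 80%, 36 for 90% and 72 for 95%. Both groups could reach 90% within the cap (36 + 36 = 72), but not 95% (72 + 72 = 144). These targets are illustrative, since the documents set none. The cap itself is therefore not the fault.

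**The case against.** A reader might infer that places are filled without regard to antibody status, or that the sample will be one-sided and the comparison must fail. The documents support neither. They are silent on how invitees and consenters are chosen, and they give no information on prevalence, vaccination or prior infection. If the smaller group is 30–50% of the sample, the difficulty largely disappears. Even with 10 in that group, a 20% error rate would show at least one discordant pair 89% of the time.

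The figures also assume a binary result, while a planned correlation suggests a quantitative one at least as readily. With quantitative results, a mostly positive sample would still test similarity across the levels it contains, so the binary figures cannot simply be carried over.

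Nor does a correlation necessarily hide an error. With 5 venous positives, one missed by the device, and 95 concordant negatives, the binary correlation is (4 × 95 − 1 × 0)/√(5 × 95 × 4 × 96) = 380/√182,400 = 0.89, which is visibly below 1. But if the device detected 80% of positives, all 5 would agree by chance with probability 0.8^5 = 33%, and the correlation would then be exactly 1.

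Finally, this is a pilot with user acceptance as its lead purpose, and status quotas belong more naturally to a validation study. That stands and lowers the severity. It does not remove the gap, because the plan still sets out to confirm similarity and has no step that would limit the claim to the people tested.

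**Conclusion.** The point holds as a conditional risk of modest severity. The plan states no rule on antibody status for filling the places, and no analysis would reveal a thin group. If results are binary and the smaller group is about 10% or less, so that it holds about 10 pairs or fewer, perfect agreement there gives an exact 95% lower limit of about 69% or below. At a 30–50% share the limit is about 88–93% and little concern remains. Which case applies cannot be read from the documents. The size rests on the assumed share, on a binary reading of the result and on all 100 places being filled.

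**What to change.** Keep the cap of 100 and make two changes.

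1. **Analysis and conclusion, in any case.** Classify each pair by the venous result from the study visit. Alongside the correlation, report device–venous agreement separately in antibody-positive and antibody-negative participants, with exact 95% intervals. If results are quantitative, also report paired differences across the observed range. Limit any conclusion of similarity to the status and range observed. This needs only a few added sentences in the analysis section and uses samples already collected.

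2. **Selection, where feasible.** If earlier parent-study serology results exist and may be used, which the documents do not state, use them to guide invitations and the choice among consenters when more than 100 sign. The aim is that both positive and negative participants are well represented as far as the cohort allows. If 100 or fewer consent, only the invitation step can act.

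The first change costs almost nothing. The second costs a record look-up, possibly a permission step and possibly slower enrolment, and the sample would no longer mirror the cohort's antibody mix. A wider antibody range can also raise a correlation without any better agreement, so the agreement results and not the correlation should carry the conclusion. No participants, visits or tests are added.

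### Correlation is the only analysis named for the paired antibody results; an ordinary coefficient measures association, not whether the two collection methods give similar results

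*Combined protocol and SAP*

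**What the plan says.** Purpose of the Study puts user acceptance first: "The purpose of this pilot study is participant user acceptance testing of the Tasso-SST OnDemand device to collect blood for antibody testing". It then adds the comparison: "The study will also compare antibody testing results from blood collected using the Tasso-SST On-Demand device compared to blood collected by phlebotomy". The title names only the comparison: "Pilot study to compare serology results from blood collected using Tasso-SST OnDemand device". Background & Significance gives the goal, which is to "confirm similar result from serum processed from blood collected by Tasso-SST OnDemand device and standard venipuncture", and the use: "Results from this pilot study will help inform the possibility of at-home specimen collection for serology testing".

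On method, Design & Procedures says "Antibody results will be compared between the two methods", which names no statistic. Data Analysis & Statistical Considerations names one analysis of the pairs: "We will evaluate correlation between results from blood collected by the two methods in this pilot study". The summary statistics mentioned there are for the survey. The document does not state:

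- which coefficient is meant;
- whether the antibody result is quantitative or positive/negative;
- any estimate of bias, limits of agreement, concordance coefficient or percent agreement.

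**The concern.** Each participant gives both samples, so the question is whether the two results from one person are close enough to be interchangeable. Read as an ordinary coefficient, correlation asks something else: whether people who are high by one method are also high by the other.

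- **Quantitative results.** Pearson r does not change with a constant or proportional bias on the scale analysed. Spearman does not change under any strictly increasing distortion. A device that reads systematically low can still give a very high coefficient.
- **Positive/negative results.** The phi coefficient falls with misclassification but does not show whether positives are missed or negatives falsely called.

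A high coefficient could therefore be reported as confirming similar results when the device reads low. The decision about at-home collection needs the size and direction of any bias, and the named analysis supplies neither.

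**Working it through.** The plan gives no figure to reproduce: no coefficient, margin or sample-size calculation, only a cap of 100 participants. Apart from that cap, every input below is an assumption chosen to show the mechanism.

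**Quantitative result, proportional bias**

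Assumed: results as log10(signal/cut-off); between-person SD 0.45; error SD 0.06 for each method; everyone drawn from the seropositive distribution; Tasso/venous ratio k.

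- Pearson r = 0.45² / (0.45² + 0.06²) = 0.2025 / 0.2061 = 0.9825. Neither k nor the centre of the distribution enters the formula, so r is the same at every ratio.
- Lin's concordance coefficient = 2 × 0.2025 / (2 × 0.2061 + (log10 k)²). At k = 0.5 this is 0.405 / (0.4122 + 0.0906) = 0.81.
- Positive agreement = P(Tasso above cut-off given venous above cut-off), from the bivariate normal distribution.

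| k | Pearson r | Lin's coefficient | Positive agreement, centre 4× | 10× | 20× |
|---|---|---|---|---|---|
| 1.0 | 0.98 | 0.98 | 98.6% | 99.7% | 99.95% |
| 0.7 | 0.98 | 0.93 | 92.2% | 98.2% | 99.6% |
| 0.5 | 0.98 | 0.81 | 82.2% | 95.1% | 98.8% |
| 0.25 | 0.98 | 0.52 | 55.1% | 82.1% | 94.0% |

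The loss at k = 0.5 is 98.6 − 82.2 = 16.4, 99.7 − 95.1 = 4.6 and 99.95 − 98.8 ≈ 1.1 percentage points. Varying the between-person SD at k = 0.5 gives, for the three centres, 85.8%, 98.9% and 99.9% with SD 0.30 (r 0.96), and 82.2%, 92.2% and 96.6% with SD 0.60 (r 0.99).

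**What an agreement analysis would show in the same data**

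- SD of the paired log10 differences = 0.06 × √2 = 0.0849.
- Limits of agreement at k = 0.5: 10^(−0.301 ± 1.96 × 0.0849) = 0.34 to 0.73.
- 95% CI of the geometric mean ratio: 0.48–0.52 with 100 pairs, 0.47–0.53 with 50, 0.46–0.55 with 20.

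The bias is plain in the ratio and invisible in r.

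**Constant shift on the raw scale**

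Simulated: 2,000,000 pairs, half seropositive centred at 4× and half seronegative at 0.15× (SD 0.30). Adding 0, 0.5 or 1.0 cut-off units to Tasso gives:

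- log-scale Pearson r 0.995, 0.969, 0.951;
- Spearman 0.992 each time;
- geometric mean ratio 1.0, 2.3, 3.3.

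Pearson r does move here, but it stays high and shows no direction.

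**Positive/negative result**

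Assumed: 50 venous positives and 50 venous negatives.

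- 9 missed positives, no false positives: phi = (41 × 50 − 9 × 0) / √(50 × 50 × 41 × 59) = 2050 / 2459 = 0.83. Positive agreement is 41/50 = 82% (exact 95% CI 69–91%).
- No missed positives, 9 false positives: phi = (50 × 41 − 0 × 9) / √(50 × 50 × 59 × 41) = 0.83. Positive agreement is 100% and negative agreement 82%.

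One coefficient describes two opposite faults.

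**The case against.** **The reading is conditional.** The plan names no coefficient, and the general statement that results will be compared rules nothing out. Correlation may have been meant loosely or as a concordance coefficient, in which case the fault is underspecification rather than a wrong choice. The condition is real. But the plan should then say so, and even a concordance coefficient falls with bias without showing its direction.

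**The result type may be known elsewhere.** The parent study's protocol, which is not supplied here, may settle it. That is possible, but it would not supply the missing agreement statistic.

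**The stakes are modest.** This is a pilot whose stated purpose is user acceptance. No threshold or decision rule is attached to the coefficient, and agreement could still be computed later from the same pairs. All of this stands, and it limits the weight of the point. Against it, the comparison is in the title, confirming similar results is the stated goal, and the repair is nearly free.

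**The illustration is assumed.** Nothing in the documents suggests a halved reading. Both samples are taken at the same visit and processed to serum for the same laboratory. The figures show what could go unseen, not what is likely.

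**The remedy has limits.** Negative agreement cannot be estimated usefully if almost everyone is positive: in the illustration the venous-positive share is 98.6% at 10× and 99.8% at 20×. A pooled ratio misdescribes an additive bias: adding 0.5 turns 0.15 into 0.65 (4.3-fold) but 4 into 4.5 (1.13-fold). Log ratios also need a rule for results below a reporting limit. These are reporting details to handle, not reasons to keep correlation alone.

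**Conclusion.** The concern holds, for the comparison aim only. Followed as written with an ordinary coefficient, the analysis could not give the size or direction of a systematic difference between Tasso and venous results, so it could not confirm that they are similar. The mathematical point does not depend on the assumed inputs. The practical size does: at a halved reading the unseen loss of positive agreement runs from about 16 points down to about 1, and is small if most results lie far above the cut-off. The conclusion rests on reading correlation as Pearson, Spearman or phi. It should be fixed before analysis.

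**What to change.** Make agreement the analysis of the paired results, keep correlation as descriptive, and state whether the result is quantitative, positive/negative or both.

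- **Positive/negative calls:** report the 2×2 table with positive and negative percent agreement of Tasso against venipuncture, each with an exact 95% CI.
- **Quantitative results:** report the geometric mean Tasso/venous ratio with 95% CI and log-scale Bland–Altman 95% limits of agreement. Plot the differences against level, and say how results below a reporting limit are handled.
- **If a concordance or absolute-agreement intraclass coefficient was intended:** name it, and still report the ratio.
- **Optional:** state beforehand what counts as similar, and add Deming or Passing–Bablok regression.

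The cost is one paragraph of text and a little more analysis of data already being collected. The figures may look less favourable than r, and intervals will be wide if positives or negatives are few. With no misses, the exact lower 95% limit, 0.025^(1/n), is 69% with 10 positives, 83% with 20 and 93% with 50; the same limits apply to negatives.
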